- A parent or guardian that consents for participation in the full length of the study
- A parent or guardian that is able to understand and comply with planned study procedures

Inclusion criteria: Mothers

- Mothers of infants that meet inclusion criteria.
- ≥ 18 years of age
- Mothers who consent to participate in the full length of the study

Exclusion criteria: Infants

- Family that is unable to participate in the full length of the study
- A diagnosis or suspicion of immunodeficiency disorder either in the infant or mother
- A diagnosis or suspicion of bleeding disorder that would contraindicate parenteral administration of MR vaccine or collection of blood by venipuncture
- Acute infection or illness at the time of enrolment (6 months) that would require infant's admission to a hospital

- Receipt of any measles or rubella containing vaccine prior to enrolment (i.e., before age 6 months) outside of study based upon documentation or parental recall
- Known history of laboratory confirmed measles or rubella infection
- A diagnosis of rubella infection in mother during pregnancy
- A diagnosis of congenital rubella syndrome in infant
- Known allergy/sensitivity or reaction to measles-rubella containing vaccine or contents of measles-rubella containing vaccine
- Persons with a history of an anaphylactic reaction to any components of the vaccine
- Infants from premature births (<37 weeks of gestation)

Exclusion criteria: Mothers

- Refuses to give blood samples. (Note: If the mother agrees for her child to participate in the study, but refuses to give a blood samples herself or blood samples cannot be obtained, the child will still be enrolled.)
- A diagnosis or suspicion of immunodeficiency disorder
- A diagnosis or suspicion of bleeding disorder that would contraindicate collection of blood by venipuncture

Temporary exclusion

- Acute febrile illness ($\geq 38^{\circ}\text{C}$) at the time of enrolment
- Family will be requested to bring back the child 1-2 days later or when child feels better.

Discontinuation criteria

Enrolled participants may be excused from the study for the following reasons:

- Withdrawal of consent for participation for any reason
- Request by parents of participant to terminate study procedures on enrolled participant
- Receipt of any measles or rubella containing vaccine (M, R, MR or MMR) outside of study based on documentation or parental recall after enrolment (6 months) or second visit at 9 months

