- Identification of immunodeficiency disorder, bleeding disorder or another medical condition for which continued participation, in the opinion of the investigator, would pose a risk to the participant to continue in the study
- Receipt of immunosuppressive medications
- Allergic reaction to a prior dose of measles or rubella containing vaccine or its contents necessitating withdrawal
- Premature termination of the study

- The participant has moved to another area outside of Matlab and is not available for follow up visits
- In case of a withdrawal from study, the local investigator should talk to a parent and document reasons why they are withdrawing, and document any adverse events or conditions that necessitate withdrawal of a participant from the study.

Termination of study

There seem to be no anticipated reasons that may result in suspension or termination of the study.

Nevertheless, there are possible causes that may warrant termination of study:

- Unexpected high number of severe adverse reactions related to use of MR vaccine or any other safety concern then any ethical committee overseeing the study, Ministry of Health or CDC can terminate the study for any safety reasons.
- A large measles or rubella outbreak in the community
- An outbreak response immunization activity with MR vaccine targeting infants aged 6 months and older in the area in response to a large measles or rubella outbreak

Measles or rubella diagnosis; measles or rubella outbreak in the community

If during the course of the study, an infant is diagnosed with a laboratory confirmed measles or rubella infection – it will not be a reason for discontinuation. If an infant is diagnosed with measles or rubella study staff will make sure that the child is non-infectious (at least 4 days after rash onset) then parents will be asked to bring the child to study site for a follow up visit

Concomitant medications and vaccines

- There will be no restrictions on the use of medications or treatments for concomitant diseases. If child is prescribed an immunosuppressive medication then the child will be excluded from the study.
- Parents will be encouraged to get their child vaccinated for other routine childhood vaccines; upon completion of the study, all parents will be reminded to take their child to their assigned vaccination centre to receive a second dose of routine measles vaccine at 15 months of age

Adherence to group assignments

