Immune response is defined as a 4-fold increase in antibody titers 12 weeks after vaccination (post-6-month visit) compared with 6-month pre-vaccine titers accounting for the expected decline in maternal antibody titers or a change from antibody-negative to positive (i.e. seroconversion). In addition, quantitative data on antibody titers will allow us to assess the magnitude of seroresponse show as $-N$ -fold increases of pre- and post-vaccine titers. Seroprotection is defined as titer of ≥ 120 mIU/mL for measles and rubella >10 IU/mL

Secondary outcomes:

Several secondary outcomes will be assessed:

- 1) Secondary outcome is based on measles titers by MBA (mIU/ml) and rubella titers (IU/mL) by ELISA on sera collected 8 weeks after MR 9-month dose of vaccination (i.e., at 11 months) – post two dose series for participants in Arm A and 1 dose for arm B.
- 2) The safety profile of MR vaccine will be assessed by incidence of specific symptoms/problems. They will be categorized into one of the following three categories:
 - a) Immediate reactions (with emphasis on allergic reactions), occurring in the first 30 minutes post vaccination observed by study staff at the fixed site clinic.
 - b) Adverse events (AE) following 6-month MR dose that may occur during the 48 hours after 6-month MR vaccine administration. AEs will be graded and subcategorized as those deemed related to vaccination or not by the investigator.
 - c) Serious adverse events (SAEs) occurring from vaccination during the course of the study, identified or observed by study staff and/or reported by parent at any time during the study period. SAEs will be subcategorized as those deemed related to vaccination or not by the investigator and reviewed by the local Data and Safety Monitoring Board (DSMB) and icddr,b ERC committee.

Data Analysis

This is an open-label trial clinical trial that compares immunogenicity of MR vaccine schedules. The study will recruit 620 participants in 2 arms. Participants will be enrolled at 6 months of age and followed at 9 months and 11 months of age for a total of 5 months of follow-up.

General analytical issues

The data will be analysed by study investigators that include epidemiologists and statisticians. Statistical packages that would be used for the analysis include R, SAS and STATA.

The immunogenicity of each MR vaccination schedule will be determined by measuring antibody levels:

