All participants will be observed for 30 minutes post vaccination to monitor for any immediate adverse reactions to the vaccine. Properly skilled medical personnel will be immediately available in case of an emergency in the event of an unexpected adverse reaction. The study physician will record at the end of this period the presence of any potential reaction to the vaccine. At the end of each study visit, the physician or study coordinator will provide the parents with a phone number for a study nurse to call if they have any questions or experience any reactions to the vaccine.

A study staff will visit the house of the participant to inquire and record any potential adverse event in 48 hours after the first dose of MR administered at 6 months (study arm A).

Should a serious illness occur while enrolled in the study (requiring a physician's visit or hospitalization), parents will be instructed to seek medical care immediately. Medical care for expected

minor illnesses that will develop during the follow up period in study participants such as rash, fever or respiratory infections as well as any adverse outcomes of the vaccination judged to be possibly, probably or definitely related (detailed below) to study vaccines or vaccination will be provided free of charge.

Recording, monitoring and reporting of adverse events

During each study visit the study staff will question the parents of the participant about possible adverse events (AE) since the previous study visit and record this in the CRF. Reported AE will be recorded in the AE form. The AE form will include a description of the event, time of onset, assessment of severity, relationship to study product, and time of resolution/stabilization of the event.

Reports of AE will be periodically discussed by the team of investigators. The study team will review the potential relationship and classify the relationship into:

1. Unable to judge
2. Not related
3. Probably not related
4. Possibly related
5. Probably related
6. Definitely related

Interpretation of vaccine-relationship to AE will be based on the type of event, the relationship of the event to the time of vaccine administration, the known biology of the vaccine and the investigators' medical judgment.

An AE will be considered a serious adverse event if it meets any of the following criteria:

1. Death during the study period
2. Hospitalization
3. Anaphylaxis associated with vaccine administration

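### The exit rules do not separate stopping study vaccine from leaving the study, and the specimen condition has no safety exemption, so adverse events in infants who leave early may be missed or dropped

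*Combined protocol and SAP*

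**What the plan says.** All references are to the combined protocol and SAP.

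**Exit.** Concomitant medications and vaccines is mandatory: "If child is prescribed an immunosuppressive medication then the child will be excluded from the study". Discontinuation criteria covers the same ground but opens permissively: "Enrolled participants may be excused from the study for the following reasons". Its list also includes immunodeficiency, an allergic reaction that makes withdrawal necessary, and "Receipt of any measles or rubella containing vaccine (M, R, MR or MMR) outside of study based on documentation or parental recall". At withdrawal the local investigator records the parents' reasons and is to "document any adverse events or conditions that necessitate withdrawal of a participant from the study".

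**Safety capture.** Secondary outcomes, item 2(c), counts serious adverse events "identified or observed by study staff and/or reported by parent at any time during the study period". The seriousness criteria under Recording, monitoring and reporting of adverse events include "Death during the study period". The same section has staff ask parents about adverse events at each study visit. Safety monitoring gives parents a nurse's telephone number.

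**Analysis.** Primary analytical approach limits the analysis of both primary and secondary objectives to infants who have not withdrawn consent and who have adequate specimens from the 6-, 9- and 11-month visits. The first secondary objective is the frequency of adverse reactions after the 6-month dose.

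**The concern.** A medical problem that appears after dosing can take an infant out of the study. If exit also ends the planned safety contacts, and the analysis then requires a full set of specimens, the safety data lose infants for reasons that cannot be assumed unrelated to the vaccine or to the risk of a later event.

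The stake is the safety record of the 6-month dose, which is given before the routine age and is a stated secondary objective. The plan compares adverse events by arm and age, and the provisions for early termination and for stopping rules set by the monitoring board depend on complete capture. Serious events are likely to be few, so one missed event can matter.

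**Working it through.** The plan states no figure on this point, so there is none to reproduce. The check is mainly a comparison of sections.

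**Step 1. The exit rules side by side.**

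| Ground | Discontinuation criteria | Elsewhere |
|---|---|---|
| Immunosuppressive medication | Permitted reason | Mandatory (Concomitant medications and vaccines) |
| Immunodeficiency, bleeding disorder or other condition | Permitted, with the qualifier "in the opinion of the investigator, would pose a risk to the participant to continue in the study" | No mandatory rule |
| Allergic reaction | Permitted, where the reaction makes withdrawal necessary | Potential risks to participants stops further MR doses after anaphylaxis and does not mention study exit |
| Measles or rubella vaccine outside the study | Permitted reason | No mandatory rule |
| Laboratory-confirmed measles or rubella | Not a reason | The infant stays and attends a follow-up visit once non-infectious |

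The first row is a direct inconsistency. No section defines stopping study vaccine as a state different from leaving the study. The last row shows that follow-up after a medical event is compatible with the design.

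**Step 2. What active safety contact is lost.** The planned contacts are 30 minutes of observation after each dose, a home visit 2 days after the 6-month dose (Arm A only), and questioning at the 9- and 11-month visits. Safety monitoring expects fever on days 7 to 12 and rash from days 7 to 10. The first planned question that can cover that window is therefore at 9 months, about three months after the dose. An Arm A infant who leaves between day 2 and the 9-month visit is never actively asked about it. The exit record covers only events that cause the withdrawal.

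**Step 3. What the analysis rule does.** Take an Arm A infant with a reaction recorded at the day-2 visit who leaves before 9 months. The infant has no 9- or 11-month specimen, so fails the condition set for secondary objectives. The infant also has one dose, while the section's intention-to-treat definition for Arm A requires two. The section mentions a safety analysis when dealing with seropositive infants but defines no population for it. Read literally, the recorded reaction is not analysed.

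**Step 4. Illustration of size, on assumptions only.** The documents give no rate for these exits and no serious-event rate. The 10% attrition allowance (31 of 310 per arm) covers all causes. Let N = 620, d = share of infants who leave on these grounds, r = serious-event risk in the others (assumed 2%), and RR = relative risk in those who leave (assumed 1 to 10). Suppose that all their events fall after exit and none is captured, which is the worst case for given d and RR.

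- Lost events = N × d × r × RR
- Lost share = d × RR / [(1 − d) + d × RR]

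| d | Infants | Lost, RR 1 | Share | Lost, RR 10 | Share |
|---|---|---|---|---|---|
| 0.5% | 3.1 | 0.06 | 0.5% | 0.62 | 4.8% |
| 1% | 6.2 | 0.12 | 1.0% | 1.24 | 9.2% |
| 2% | 12.4 | 0.25 | 2.0% | 2.48 | 16.9% |

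For example, with d = 1% and RR = 10: lost = 620 × 0.01 × 0.02 × 10 = 1.24; total = 613.8 × 0.02 + 1.24 = 13.52; share = 1.24 / 13.52 = 9.2%. If half of the later events are still reported, each loss halves. At r = 5% the counts are 2.5 times larger and the shares are unchanged.

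**The case against.** The strongest reply is that the gap is narrow and partly covered.

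- **Exit is mostly discretionary.** Only the immunosuppressant rule is mandatory. A reader might infer that every infant on the listed grounds is dropped automatically; the permissive opening and the qualifiers do not support that. This stands.
- **Reporting does not close at exit.** Nothing ends parent or staff reporting of serious events, the nurse's number remains, and events that cause withdrawal are recorded. It would be too strong to say that safety follow-up ends or that later events are not collected. This stands, but a passive route is weaker than scheduled questioning, and no section extends questioning past exit.
- **These are not shown to be the infants at most risk.** Infants with diagnosed or suspected immunodeficiency are already excluded at entry. For infants given an extra dose, Potential risks to participants says that adverse events other than anaphylaxis are less likely after a second dose. The rules also cover both arms, and Arm B has no study dose before 9 months. This stands, and with it falls any claim that the 6-month dose is shown to look safer than it is.
- **Exit a month after dosing falls outside the expected reaction window.** True of onset. It does not answer Step 2, because the question about that window would be asked only at 9 months.
- **It is too late to add contacts.** Special Assays or Procedures describes the assay change as following completion of field data collection. This probably stands for new contacts. It does not affect the analysis population, which can still be defined.

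**Conclusion.** The concern holds as a gap in definition and a possible undercount, not as a demonstrated bias. Three things are established from the text: the exit rules conflict for immunosuppressive medication; stopping vaccine is not separated from leaving the study, so active questioning has no stated basis after exit; and the specimen condition, read literally, can remove events already recorded.

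That adverse and serious adverse events may be undercounted, in a way related to medical course after dosing, is an inference from these. Its size cannot be taken from the documents. It is probably a few infants, and the illustration (0.06 to 2.48 expected serious events, or 0.5% to 16.9%) rests wholly on assumed exit rates, risks and complete loss after exit. The plan should be corrected because the remedy is cheap and its main part is still feasible.

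**What to change.** 1. **Define a safety population.** Include every infant who received at least one study dose, kept in the randomised arm. Where arms are compared before the 9-month dose, use Arm B infants over the same period as comparator, for events sought in both arms (the day-2 home visit is Arm A only). Exempt this population from the specimen condition in Primary analytical approach. Include all events recorded before exit and any reported passively afterwards. Report exits by arm, reason and last safety contact.
2. **Reconcile the exit rules.** Discontinuation criteria and Concomitant medications and vaccines must agree on immunosuppressive medication. Define discontinuation of study vaccine separately from withdrawal from the study.
3. **If any follow-up is still open,** continue adverse-event questioning at the scheduled 9- and 11-month contacts after vaccine discontinuation. Exceptions are withdrawn consent, a parental request to stop procedures, moving out of reach, and termination of the study.

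None of this changes who is vaccinated. The cost is revised wording, a few extra adverse-event forms if item 3 applies, and a safety denominator slightly different from the immunogenicity one.

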During large measles outbreaks, WHO recommends using an MCV starting at 6 months to prevent measles among young infants. This dose of MCV should be considered only as MCV 0 dose and parents are advised to bring their infants to receive a routine MCV first dose at 9 months. Most studies of immunogenicity of measles containing vaccine in infants <9 months were conducted using a measles single antigen vaccine. There is a limited data on immunogenicity of MR vaccine administered at < 9 months of age and its impact on immunogenicity of MR vaccine routinely administered at 9 months. As more countries are introducing MR vaccine in their routine immunization program (at 9 months) we propose a study that will assess the immunogenicity of MR vaccine at 6 months (MCV 0 dose) and its impact on immunogenicity of MR vaccine administered at 9 months (MCV1 dose).

Relevance:

The primary purpose of the study is to assess the immunogenicity of MR vaccine when delivered at 6 months. In addition, the study will establish the equality of MR vaccine seroconversion administered at 9 months following administration of an earlier MR vaccine dose at 6 months of age compared to MR vaccine dose administered at 9 months without previous MR vaccination. This study will also provide additional data on safety and tolerance of MR vaccine given at 6 months, and impact of maternal antibodies on immunogenicity of MR vaccine at 6 months.

Hypothesis:

Our study hypothesis is that the proportion of children seroconverting after administration of MR vaccine dose at 9 months, and who had received an MR vaccine dose at 6 months of age, is not different from that obtained after administration of MR vaccine dose at 9 months in infants who had no previous dose of MR vaccine.

Primary objectives:

1. To assess immunogenicity of MR vaccine at 6 months of age
2. To assess immunogenicity of MR vaccine at 9 months of age among children without prior measles and rubella vaccination, compared with MR vaccine immunogenicity among those who had a prior MR vaccination at 6 months of age

Secondary objectives:

1. To assess the frequency of adverse reactions following administration of MR vaccine at 6 months
2. To compare the immunogenicity of the MR vaccine first dose administered at 6 months vs at 9 months.
3. To assess the proportion of mothers with undetectable, detectable and protective levels of measles and rubella antibodies

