2. A study doctor will obtain a medical history and conduct a medical examination to assess whether the infant is eligible to take part in the study.
3. Infants who are not eligible per inclusion and exclusion criteria will be excused from study participation and it will be documented in the case reporting form.

4. Participants who meet temporary exclusion criteria at enrollment will be excused for the day and will be requested to return several days later, but as long as their age is 180 days, +/- 7 days. A note will be made in the case reporting form.
5. The eligible infant will be given a study ID and assigned to a study arm (arm A or B) according to a pre-determined randomization scheme. Further details of the randomization scheme are described in the 'Data Analysis' section.
6. Parents will be interviewed and socio-demographic and clinical information will be collected as per standardized study questionnaire.
7. One blood specimen (minimum of 1 ml) will be collected by venipuncture from all enrolled infants following the enrollment. During visits in which the child receives vaccine, blood samples will be drawn before vaccine administration.
8. One blood specimen (1 ml) will be collected by venipuncture from mothers of all enrolled infants following the enrollment.
9. Infants randomized to the study arm A will be administered the first dose of MR vaccine. Vaccine will be administered only if an adequate blood specimen has been collected from the participant.
10. The participant will be observed for 30 minutes for any adverse reactions from administration of the vaccine or the blood collection.
11. A research assistant will schedule the second visit. All participants will be requested to return 3 months later after enrolment, i.e., at 9 months of age.

Follow up home visit (2 days after MR vaccination). Safety monitoring.

- Children in study arm A, who received a 6 month dose of MR vaccine, will be visited by a field research assistant at their homes 2 days after MR vaccination. This visit is to identify if any participants experienced any adverse events following immunization.
- The research assistant will inquire about and record any potential adverse events after the 6 month dose of MR. All finding will be captured in the AEFI form.

Study site visit at 9 months of age. Blood draw and MR vaccination.

During the 9 month visit, the following procedures will be conducted:

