7. Any additional medical records
8. Measures to ensure protection of study participants
9. Measures to ensure compliance with study protocol, and accuracy and completeness of records

10. Any regulatory files associated with the study will also be inspected to ensure all regulatory and reporting requirements are being followed

Site monitoring visits will be conducted by CDC staff that have not interacted with study participants.

Site monitoring reports will be shared with site PI.

Safety monitoring

Live attenuated measles vaccines currently in use have an excellent track record for safety and efficacy.

Measles vaccine was introduced in Bangladesh in 1979 and since then has been used widely in the country. Recently, Bangladesh conducted a nationwide MR SIA targeting 52 million children aged 9 months – 15 years of age in 2014, and introduced MR into the routine immunization schedule.

Few children may experience some adverse effects from MR vaccine. Most adverse effects are mild and transient (local reaction at injection site, fever, and rash) with no long term sequelae. One serious but very rare adverse effect of measles vaccine is anaphylaxis following vaccination.

Fever of 39.4° C or higher ($\geq 103^{\circ}$ F) occurs in approximately 5% to 15% of vaccine recipients between the 7th and 12th day after vaccination and lasts approximately 1 to 2 days. (4) Rash occurs in approximately 5% of recipients, beginning 7 to 10 days after vaccination and lasting for 1 to 3 days. Determining the etiology of a rash illness after measles vaccination can be difficult because other infections, such as human herpesvirus type 6 and human parvovirus type 19, can often occur early in life and can be confused with a vaccine reaction. (4)

The rate of anaphylaxis is approximately 1 to 3.5 per million doses administered. Children with immediate hypersensitivity to eggs can be safely immunized with measles vaccines, and no special precautions are necessary.(4)

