MR vaccine (dose is 0.5ml) per WHO EPI immunization guidelines will be administered following all safety norms. The most common side-effect of MR vaccine injection is pain and redness at the site of administration. The site will be used for monitoring of local reactions.

MR vaccine may have some traces of neomycin. Rarely participants may react to these substances through these reactions. One serious but extremely rare adverse effect to measles vaccine is anaphylaxis. The risk is extremely low - 1 in 3.5 million doses administered(4). Overall, adverse events, with the exception of anaphylactic reactions, are less likely to occur after receipt of a second dose of measles containing vaccine.

It is important to recognize the early symptoms of anaphylaxis and treat such cases immediately. Therefore all infants who receive study vaccine dose will be observed for 30 minutes by medical officer and if any signs of anaphylactic reaction are noticed the medical officer will initiate treatment on the site. Treatment will be free of charge. This child will not receive future MR vaccine doses. Special notes will be made in his medical card. Although we do not expect any additional side effects the 6 months infants will be followed for 48 hours after receipt of the first MR study dose because they receive MR vaccination before the age of routine vaccination in Bangladesh. Most common adverse events in infants at 6 months after administration of measles containing vaccine are fever, mild rash, redness and swelling of injection site. Most adverse effects are mild and self-limited.

Forty eight hours after vaccine administration at 6 month a study staff will visit respondents at their home to monitor and document any adverse effects following immunization.

All costs will be provided by the study for infants who experience severe adverse events in this study.

Participant Privacy

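### The 6-month-dose safety outcome stops at 48 hours, before the fever and rash that the protocol itself expects, so it cannot serve as the frequency of adverse reactions named in secondary objective 1

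*Combined protocol and SAP*

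**What the plan says.** The objective, listed under Secondary objectives in the Project Summary and again under Specific Objectives, is "To assess the frequency of adverse reactions following administration of MR vaccine at 6 months". It carries no 48-hour limit. Under Time to endpoint, the time frame for this objective runs from randomization to 11 months.

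The data collection is narrower. Under Study procedures, the follow-up home visit is for Arm A children, who "will be visited by a field research assistant at their homes 2 days after MR vaccination". The Safety monitoring and Potential risks sections restate this contact as 48 hours after the dose. Under Secondary outcomes there are three safety categories: immediate reactions in the first 30 minutes, adverse events "that may occur during the 48 hours after 6-month MR vaccine administration", and serious adverse events at any time in the study.

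The protocol also says when reactions are due. Its Safety monitoring section puts fever of 39.4 °C or higher "between the 7th and 12th day after vaccination and lasts approximately 1 to 2 days", in about 5% to 15% of recipients. It puts rash in about 5%, "beginning 7 to 10 days after vaccination and lasting for 1 to 3 days". The Potential risks section applies this to the age group: "Most common adverse events in infants at 6 months after administration of measles containing vaccine are fever, mild rash", followed by redness and swelling at the injection site.

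Later solicited information comes from the clinic visits: "During each study visit the study staff will question the parents of the participant about possible adverse events (AE) since the previous study visit". The first of these after the 6-month dose is at 9 months of age.

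**The concern.** The one active contact and the outcome window both close before the systemic reactions named in the protocol are due to start. A fever on day 9 that does not lead to hospital admission fits none of the three safety categories: it is not immediate, it is not within 48 hours, and it is not serious under the protocol's definition (death, hospitalization or anaphylaxis).

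What is at stake is how the result is read. The Relevance section promises further safety and tolerance data on the dose at 6 months, an age at which the vaccine is recommended in outbreaks. A low 48-hour count, reported as the frequency of adverse reactions, could be cited as evidence that fever and rash are uncommon after the early dose, although observation ended before they were expected. The Possible limitations section does not mention this.

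**Working it through.** **Inputs**
- Arm A enrolment: 310 (Sample size section). The plan's figure reproduces as 279 / (1 − 0.10) = 310.
- Home visit: day 2 (Study procedures).
- Fever of 39.4 °C or higher: 5% to 15%, days 7 to 12, lasting about 1 to 2 days (Safety monitoring).
- Rash: about 5%, onset days 7 to 10, lasting 1 to 3 days (Safety monitoring).
- Next scheduled contact: 3 months after enrolment, taken here as day 90. The protocol allows 7 days either side of 9 months of age.

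**Timing**
- From visit to earliest expected onset: 7 − 2 = 5 days. The visit cannot record any event in either window.
- From fever onset to the 9-month visit: 90 − 12 = 78 days to 90 − 7 = 83 days, or about 11 to 12 weeks. With the visit at day 83 or day 97, the extremes are 83 − 12 = 71 and 97 − 7 = 90 days.
- The episodes last 1 to 3 days, and the documents describe no diary.

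**Expected events outside the 48-hour outcome (n × rate)**

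| | n = 310 enrolled | n = 279 after attrition |
|---|---|---|
| Fever at 5% | 15.5 | 14.0 |
| Fever at 15% | 46.5 | 41.9 |
| Rash at 5% | 15.5 | 14.0 |

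That is about 16 to 47 fevers and about 16 rashes among 310 infants.

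**Sensitivity to age.** The rates are given for vaccine recipients in general. Suppose, as an assumption, that reactions scaled with vaccine response, and take the 50% seroconversion at 6 months assumed in the Sample size section as the scaling factor. The counts would halve: 15.5 × 0.5 = 7.8 to 46.5 × 0.5 = 23.3 fevers (about 8 to 23), and about 8 rashes. The timing result is unchanged.

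**Is sample size the problem?** No. Had the window been covered, the 95% half-width 1.96 × √(p(1 − p)/310) would be 2.4 percentage points at p = 5% and 4.0 points at p = 15%. The limit comes from when events are ascertained.

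**The case against.** Four counter-arguments deserve weight.

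1. **The plan already defines a 48-hour outcome.** It does, and that window suits injection-site reactions. The Potential risks section calls pain and redness at the site the most common side-effect, so early local reactions are adequately covered. But the objective and its listed time frame are wider than the outcome, and the same section names fever and mild rash among the common events at 6 months. The mismatch stands.

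2. **Other reporting routes exist.** Parents have a nurse's phone number, care for rash and fever is free, and serious events are captured at any time. A reader might infer that later fevers and rashes would go wholly unobserved, or that recall is the only source. The documents do not support that. Recall is the only *solicited* later source. The other routes depend on parents coming forward or cover serious events only, so they do not yield a frequency.

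3. **The direction of error in recalled data is not established.** A reader might infer that recalled fever must be biased low. Short episodes can be forgotten, but a question covering three months also picks up unrelated illness. The documents contain nothing from which to estimate the completeness of recall. Arm B parents are asked the same question at 9 months, which gives a concurrent background. That background is imperfect, because the trial is open-label and only Arm A has the home visit.

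4. **Collection cannot now be changed.** The change note under Special Assays or Procedures says that field data collection is complete. A remedy that alters follow-up is therefore not available for this trial, and this review proposes no visit timing. What remains is a matter of definition and reporting. That makes it cheap to correct but does not remove it.

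**Conclusion.** The concern holds as a mismatch between objective and outcome. The pre-specified non-serious outcome for the 6-month dose ends 5 days before the earliest fever or rash onset that the protocol expects. At the protocol's own rates, about 16 to 47 high fevers and about 16 rashes among 310 Arm A infants fall outside it, or about half that if reactions track the assumed 50% response. The timing conclusion rests only on the protocol's stated windows. The counts rest on applying general vaccine-recipient rates to 6-month-olds.

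The 48-hour data can support a statement about immediate and early, mainly local, reactions. They cannot support one about the frequency of vaccine-associated fever or rash. The point concerns one secondary objective; the primary immunogenicity objectives are unaffected. It should be corrected before results are reported, because it decides what may be claimed about the tolerability of the early dose.

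**What to change.** - Reconcile the objective, its time frame under Time to endpoint, the Secondary outcomes definition, and the home-visit descriptions in Study procedures, Safety monitoring and Potential risks with the onset windows given in Safety monitoring.
- Since collection is complete, restate secondary objective 1 and its outcome as immediate reactions (30 minutes) and reactions within 48 hours of the 6-month dose.
- Report non-serious events recalled at the 9-month visit separately, labelled as recalled. Show Arm B's reports for 6 to 9 months beside them as background, and note the open-label design and the Arm A home visit.
- Add to Possible limitations that the trial does not reliably estimate the frequency of vaccine-associated fever or rash after the 6-month dose, and that a low 48-hour rate is not evidence of their absence.

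The cost is a few sentences of text and one additional table, with no new data and no change to sample size. The price is a narrower safety conclusion.
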